3.5 COST AND COMPENSATION

3.5.1 Costs

NIH does not bill health insurance companies or participants for any research or related clinical care that participants receive at the NIH Clinical Center. If some tests and procedures are performed outside the NIH Clinical Center, participants may have to pay for these costs if they are not covered by an insurance company. Medicines that are not part of the study treatment will not be provided or paid for by the NIH Clinical Center.

3.5.2 Compensation

Subjects will not receive compensation for participation in this study.

3.5.3 Reimbursement

The NCI will cover the costs of some expenses associated with protocol participation. Some of these costs may be paid directly by the NIH and some may be reimbursed to the participant/guardian as appropriate. The amount and form of these payments are determined by the NCI Travel and Lodging Reimbursement Policy.

3.6 CRITERIA FOR REMOVAL FROM PROTOCOL THERAPY AND OFF STUDY CRITERIA

Regardless of reason for removal from study therapy, participants will be asked to have a 28 day follow up safety visit. Participants who are unable or unwilling to return for this visit will be asked to review any safety concerns by phone within this time period.

3.6.1 Criteria for Removal from Protocol Therapy

- Completion of protocol therapy.
- Clinical or radiographic progression of disease except when the investigator feels the subject is still benefiting from treatment. (It is generally preferable for participants to remain on treatment past initial radiographic progression in case there is pseudo - progression, except when the investigator feels that the clinical picture warrants changing therapy at initial progression).
- Unacceptable toxicity possibly attributed to all active therapies (see Section [3.3](#)).
- Participant requests to be withdrawn from active therapy.
- Start of another systemic anticancer treatment or participation in another investigational therapeutic trial (except for standard of care therapy for phase II participants). For participants enrolled in the phase I portion of the protocol, focal palliative radiotherapy, ablation, or surgery to a site of disease will not necessitate removal from protocol therapy.
- Investigator discretion.
- Positive pregnancy test.
- Intercurrent illness that prevents further administration of treatment, in the judgement of the investigator.

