6. Participants who have come off treatment for disease progression will be followed by phone annually for survival. Participants who have not progressed on treatment will continue to be followed and scanned per investigator discretion until progression. Initial and follow up courses of treatment may extend beyond a year per investigator discretion.

7. As indicated in Section **12.3**, all subjects will be offered the opportunity to complete an NIH advanced directive form. This should be done preferably at baseline but can be done at any time during the study as long as the capacity to do so is retained. The completion of the form is strongly recommended, but is not required.

8. Biochemical profile: Acute care, hepatic and mineral panel as described in Sections **2.2** and **2.4**.

9. Evaluate CEA, CA19-9, CA125 and CA15-3 at baseline and follow elevated values thereafter (for participants enrolled on the phase I portion of the protocol).

10. In HIV positive participants.

11. Every 8 weeks for participants.

12. Imaging will be performed every 8 weeks. In the event of a PR or CR tumor imaging assessments may be performed every 3 months (+/- 2 weeks) at the discretion of the investigator. Tumor assessment should be continued beyond end of treatment in participants who have not experienced PD until they experience PD in order to assess PFS. MRI (with gadolinium) will be used when CT scan is not an option to follow the disease. Bone scans and other imaging assessments may also be performed as clinically indicated.

13. In participants with known CNS disease as described in Section 2.1.2.3; MRIs may be performed as clinically indicated in this population.

14. Where feasible, optional biopsies may be done at baseline and at week 9 and will likely be CT guided. If a recent (\leq 6 months preferred) outside biopsy has been performed that specimen may be used in lieu of a baseline biopsy for both phase I and II participants.

15. Where feasible, research blood (see Section 5.1) will be collected at the following time points:

- PKs and ADAs – performed only on Arm 1B (bintralusp alfa plus vaccine)
 - Samples for PK analysis will be taken prior to infusion and following infusion on W1 and W5 and prior to infusion on W3 and W11 or with end of treatment labs if patients comes off treatment prior to any of those timepoints; and

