4 CONCOMITANT MEDICATIONS/MEASURES

4.1 PERMITTED MEDICATIONS

Any medications (other than those excluded by the clinical trial protocol) that are considered necessary to protect subject welfare or alleviate symptoms and will not interfere with the trial medication may be given at the Investigator's discretion.

Palliative radiotherapy delivered in a normal organ-sparing technique may be administered during the trial. The assessment of PD will not be based on the necessity for palliative radiotherapy.

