6.3 RESPONSE CRITERIA

6.3.1 Antitumor Response

Tumor assessments may include the following evaluations: physical examination (with photograph and measurement of skin lesions, as applicable); cross-sectional imaging using computed tomography (CT) or magnetic resonance imaging (MRI) scan of the chest, abdomen, and pelvis (pelvis scan is optional unless known pelvic disease is present at baseline); nuclear bone scan for subjects with known/suspected bone lesions; and CT or MRI scan of the brain (only as clinically warranted based on symptoms/findings). The preferred method of disease assessment is CT with contrast. If CT with contrast is contraindicated, CT of the chest without contrast and MRI scan of the abdomen/pelvis is preferred.

At baseline, tumor lesions will be selected and categorized as target or non-target lesions. Target lesions include those lesions that can be accurately measured in at least 1 dimension as ≥ 20 mm with conventional techniques or ≥ 10 mm with CT scan. Malignant lymph nodes with a short axis diameter ≥ 15 mm can be considered target lesions. Up to a maximum of 2 target lesions per organ and 5 target lesions in total will be identified at baseline. These lesions should be representative of

all involved organs and selected based on their size (those with the longest diameter) and their suitability for accurate repeated measurements. A sum of the longest lesion diameter (LLD) for all target lesions will be calculated and reported as the baseline sum LLD. For malignant lymph nodes identified as target lesions, the short axis diameter will be used in the sum of LLD calculation. All other lesions (or sites of disease) should be identified as non-target lesions (including bone lesions).

All post-baseline response assessments should follow the same lesions identified at baseline. The same mode of assessment (e.g., CT) used to identify/evaluate lesions at baseline should be used throughout the course of the study unless subject safety necessitates a change (e.g., allergic reaction to contrast media).

For the primary endpoint antitumor activity will be evaluated with target and/or non-target lesions according to RECIST Version 1.1.

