6.3.5 Response Criteria by RECIST 1.1

6.3.5.1 Evaluation of Target Lesions

Complete Response (CR): Disappearance of all target lesions. Any pathological lymph nodes (whether target or non-target) must have reduction in short axis to <10 mm.

Partial Response (PR): At least a 30% decrease in the sum of the diameters of target lesions, taking as reference the baseline sum of diameters.

Progressive Disease (PD): At least a 20% increase in the sum of the diameters of target lesions, taking as reference the smallest sum on study (this includes the baseline sum if that is the smallest on study). In addition to the relative increase of 20%, the sum must also demonstrate an absolute increase of at least 5 mm. (Note: the appearance of one or more new lesions is also considered progressions).

Stable Disease (SD): Neither sufficient shrinkage to qualify for PR nor sufficient increase to qualify for PD, taking as reference the smallest sum of diameters while on study.

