6.3.5.3 Evaluation of Best Overall Response

The best overall response is the best response recorded from the start of the treatment until disease progression/recurrence (taking as reference for progressive disease the smallest measurements recorded since the treatment started). The participant's best response assignment will depend on the achievement of both measurement and confirmation criteria.

For Participants with Measurable Disease (i.e., Target Disease)

Target Lesions	Non-Target Lesions	New Lesions	Overall Response	Best Overall Response when Confirmation is Required*
CR	CR	No	CR	≥ 4 wks. Confirmation**
CR	Non-CR/Non-PD	No	PR	≥ 4 wks. Confirmation**
CR	Not evaluated	No	PR	
PR	Non-CR/Non-PD/not evaluated	No	PR	
SD	Non-CR/Non-PD/not evaluated	No	SD	Documented at least once ≥ 6 wks. from baseline**
PD	Any	Yes or No	PD	no prior SD, PR or CR
Any	PD***	Yes or No	PD	
Any	Any	Yes	PD	

Target Lesions	Non-Target Lesions	New Lesions	Overall Response	Best Overall Response when Confirmation is Required*
*	See RECIST 1.1 manuscript for further details on what is evidence of a new lesion.			
**	Only for non-randomized trials with response as primary endpoint.			
***	In exceptional circumstances, unequivocal progression in non-target lesions may be accepted as disease progression.			
Note:	Participants with a global deterioration of health status requiring discontinuation of treatment without objective evidence of disease progression at that time should be reported as “ symptomatic deterioration .” Every effort should be made to document the objective progression even after discontinuation of treatment.			

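### Phase I permits local therapy to target lesions, but no response rule says how a treated lesion is scored, so local shrinkage or removal can count as a response to study treatment

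*Combined protocol and SAP*

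**What the plan says.** **Permission.** For Phase I, section 3.6.1 states that "focal palliative radiotherapy, ablation, or surgery to a site of disease will not necessitate removal from protocol therapy". Section 4.1 adds, for radiotherapy only, "Palliative radiotherapy delivered in a normal organ-sparing technique may be administered during the trial" and "The assessment of PD will not be based on the necessity for palliative radiotherapy". Neither section restricts local treatment to non-target lesions. Section 3.3.2 allows dosing delays for palliative radiation, and Table 7 allows elective surgery on study, so the plan expects some local treatment.

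**Scoring.** Section 6.3.1 requires that "All post-baseline response assessments should follow the same lesions identified at baseline". Section 6.3.5.1 defines PR as "At least a 30% decrease in the sum of the diameters of target lesions, taking as reference the baseline sum of diameters". Section 6.3.5.3 sets the window: "The best overall response is the best response recorded from the start of the treatment until disease progression/recurrence". Section 6.3.4 asks for a confirmatory scan no sooner than 4 weeks after a PR or CR.

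**Analysis.** Section 10.3 makes a participant evaluable for response if disease was measurable at baseline and was re-evaluated. Sections 10.4.4 (duration of response), 10.4.4.1 (PFS) and 10.4.4.2 (objective response) do not mention local or subsequent anticancer therapy.

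**The concern.** Each provision is reasonable alone. Together they let a change made by a surgeon, an ablation or a radiation field enter the target-lesion sum as if study treatment had caused it. The permission is explicit, the instruction to keep following the same lesions is explicit, and nothing connects the two.

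ORR, duration of response and PFS are Phase I secondary endpoints (sections 1.1.2 and 10.1.2.1). Section 10.4.1 expands Arm 1B to 10 evaluable participants to obtain an early view of the combination's efficacy. In a group that small, one misattributed response visibly changes the reported rate.

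**Working it through.** **Inputs.** From the plan: PR threshold of a 30% fall from the baseline sum; PD as a rise of at least 20% and at least 5 mm from the smallest on-study sum (6.3.5.1); at most 5 target lesions (6.3.1); 10 evaluable in Arm 1B (10.4.1); up to 22 in Phase I (10.2). Lesion sizes and the number or share of affected participants are my assumptions, since the plan gives none.

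**Plan's own figure.** Taking the 3+3 maximum of 6 at each of two monotherapy levels plus 10 in Arm 1B, 6 + 6 + 10 = 22, as stated. The plan gives no target rate or precision for ORR.

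**Can local therapy alone create a PR?** Let S be the baseline sum, L the baseline diameter of a removed target lesion, and g the growth factor of the remaining targets. The new sum is (S - L) × g, and PR requires (S - L) × g ≤ 0.70 × S.
- S = 100 mm, L = 35 mm, g = 1.00: the sum is 65 mm, or -35%. This is a PR although the untreated targets did not change.
- S = 100 mm, L = 40 mm, g = 1.15: the sum is 60 × 1.15 = 69 mm, or -31%. This is a PR although every untreated target grew.

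The second case survives an intermediate scan. If 60 mm was recorded first, that is -40%, and the later 69 mm is 69/60 = +15% from nadir, below the PD threshold. With no new lesion and no unequivocal non-target progression, both scans read PR and, if at least 4 weeks apart, confirm each other.

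With g = 1, any lesion holding at least 30% of the baseline sum is enough. With three or fewer target lesions, the largest always holds at least one third.

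**Effect of one case on ORR.** One of 10 is 10 percentage points. The exact (Clopper-Pearson) 95% interval for x of n runs from the 0.025 quantile of Beta(x, n - x + 1) to the 0.975 quantile of Beta(x + 1, n - x).
- 2/10 = 20%, interval 2.5% to 55.6%
- 3/10 = 30%, interval 6.7% to 65.2%

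Over all 22 Phase I participants, one case is 1/22 = 4.5 points.

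**Range.** Suppose a share q of true non-responders is scored as responding because of local therapy. The expected ORR is p + (1 - p) × q, where p is the true rate.

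| True ORR p | q | Expected ORR | P(at least 4 of 10) |
|---|---|---|---|
| 20% | 0 | 20% | 0.121 |
| 20% | 5% | 24% | 0.201 |
| 20% | 10% | 28% | 0.298 |
| 20% | 20% | 36% | 0.513 |
| 30% | 0 | 30% | 0.350 |
| 30% | 5% | 33.5% | 0.445 |
| 30% | 10% | 37% | 0.540 |
| 30% | 20% | 44% | 0.712 |

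**PFS and duration of response.** Take two targets of 50 mm each (assumed), baseline sum 100 mm.
- *PD brought forward.* One lesion is ablated, so the nadir becomes 50 mm. The other grows to 60 mm: +20% and +10 mm, which is PD. Without ablation, 100 to 110 mm is +10%, not PD.
- *PD postponed.* One lesion grows to 65 mm (sum 115 mm, +15%) and is then ablated; the sum falls to 50 mm. Left alone and reaching 70 mm, it would have given 120 mm, +20%, which is PD.

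The direction therefore depends on which lesion is treated.

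**The case against.** **RECIST 1.1 may already cover this.** Sections 6.3.4 and 10.4.4.2 score response under RECIST 1.1, and the instruction to follow the same lesions can be read as a consistency requirement, not as crediting local therapy. This stands in part: the plan nowhere instructs anyone to count a resected lesion as a response. But section 6.3 writes out its own lesion and response rules, none of which addresses treated lesions, and what the cited guideline says cannot be established from these documents. Two assessors could score the same scans differently.

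**Much local therapy will not touch the sum.** Section 6.3.2 makes bone lesions non-measurable and section 6.3.1 lists them as non-target, so bone-directed radiotherapy does not alter it. This stands. The exposure is resection, ablation or irradiation of a measurable target lesion before PD.

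**The consequences are limited.** These endpoints are secondary and carry no test or decision threshold, Arm 2B is closed, and the intervals for 2/10 and 3/10 overlap almost entirely. All of this stands and limits the severity.

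**Next-line responses.** A reader might infer that responses to later systemic therapy also count, because note 12 of section 3.4.1 says "Tumor assessment should be continued beyond end of treatment in participants who have not experienced PD until they experience PD". The documents do not support that inference. The note gives PFS as the purpose of those scans, section 4.2 prohibits other systemic anticancer treatment in Phase I, and starting it ends protocol therapy under 3.6.1. The plan is silent on whether such scans enter best overall response, which merits a clarifying sentence only.

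**Conclusion.** The concern holds for response rate. The permission in 3.6.1 combined with the rules in 6.3.1, 6.3.5.1 and 6.3.5.3 allows a target lesion removed or shrunk by local therapy before PD to be scored as a CR or PR, and the confirmation requirement does not prevent it. One case moves Arm 1B ORR by 10 points. That one case is an assumption, because the plan gives no frequency of local therapy; the shares in the table are assumptions too.

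A reader might infer that the error always flatters the treatment. For PFS and duration of response it does not: removing a lesion also lowers the nadir against which PD is judged, so progression can be called sooner as well as later.

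The Phase I safety and RP2D endpoint and the Phase II CD3+ endpoint are unaffected. The point should be corrected before the Phase I efficacy results are analysed, but it does not threaten the trial's main conclusions.

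**What to change.** Add to sections 6.3.5.3 and 10.4.4.2:
- A CR or PR counts only if its criteria were first met before any local therapy to a target lesion.
- After local therapy, that target lesion is not evaluable for shrinkage; PD elsewhere still counts.
- Assessments after the start of other systemic anticancer therapy do not contribute to best overall response.

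Add to sections 10.4.4 and 10.4.4.1 one pre-specified sensitivity analysis of duration of response and PFS for participants who had such therapy before PD, for example censoring at its start. Treating its start as an event is harder to reconcile with section 4.1, under which needing palliative radiotherapy is not PD.

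**Cost.** A few sentences, with no change to sample size. An occasional response assessment is lost, and ORR may look slightly less favourable. Dates and sites of local therapy and dates of subsequent therapy must be captured. The Phase I calendar collects concomitant medications only through safety follow-up and lists no item for procedures or later therapies, so a data field may be needed. The clinical permission for local treatment is unchanged.

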3.6.2 Off-Study Criteria

- Failure to maintain eligibility criteria prior to starting treatment.
- Screen failure.
- PI decision to end the study.
- Participant requests to be withdrawn from study.
- Participant lost to follow-up.
- Investigator discretion.
- Death.
- Completion of 5-year follow up period. (Only for Phase II)

3.6.3 Lost to Follow-up

A participant will be considered lost to follow-up if he or she fails to return for 4 scheduled visits and is unable to be contacted by the study site staff.

The following actions must be taken if a participant fails to return to the clinic for a required study visit:

- The site will attempt to contact the participant and reschedule the missed visit within the next 2 weeks and counsel the participant on the importance of maintaining the assigned visit schedule and ascertain if the participant wishes to and/or should continue in the study.
- Before a participant is deemed lost to follow-up, the investigator or designee will make every effort to regain contact with the participant (where possible, 3 telephone calls and, if necessary, an IRB approved certified letter to the participant's last known mailing address or local equivalent methods). These contact attempts should be documented in the participant's medical record or study file.
- Should the participant continue to be unreachable, he or she will be considered to have withdrawn from the study with a primary reason of lost to follow-up.

4 CONCOMITANT MEDICATIONS/MEASURES

4.1 PERMITTED MEDICATIONS

Any medications (other than those excluded by the clinical trial protocol) that are considered necessary to protect subject welfare or alleviate symptoms and will not interfere with the trial medication may be given at the Investigator's discretion.

Palliative radiotherapy delivered in a normal organ-sparing technique may be administered during the trial. The assessment of PD will not be based on the necessity for palliative radiotherapy.

4.2 PROHIBITED MEDICATIONS

The following treatments should not be administered during the trial:

- Other immunotherapies or immunosuppressive drugs (for example, chemotherapy or systemic corticosteroids except for prophylaxis or treatment of allergic reactions, endocrine replacement therapy at low dose prednisone [≤ 10 mg daily] or equivalent, for the treatment of irAEs, or for short courses (≤ 14 days) as appropriate medical therapy for

unrelated medical conditions (e.g., asthma). Steroids with no or minimal systemic effect (topical, inhalation) are allowed.

- Prophylactic use of corticosteroids for infusion related reactions. Corticosteroid administration prior to CT scans in participants with intravenous contrast allergy is allowed.
- Any live vaccine therapies for the prevention of infectious disease. Administration of inactivated vaccines is allowed (for example, inactivated influenza vaccines or locally approved COVID vaccines).
- Systemic anticancer treatment (except standard of care therapy for phase II participants).

5 CORRELATIVE STUDIES FOR RESEARCH**5.1 BIOSPECIMEN COLLECTION**

Test/assay	Volume (approx.) per Timepoint	Type of tube ^a	Collection point	Location of specimen analysis
Standard and 123 immune cell subsets by FACS			See Study Calendar	LTIB [Storage at Clinical Services Program (CSP)]
Functional Analysis of immune cell subsets by FACS	60-80 mL blood for PBMCs	Sodium heparin (green top) tubes		LTIB (Storage at CSP)
Antigen Specific Immune Response by cytokine staining assay				LTIB (Storage at CSP)
T cell clonality by immuno-seq platform				LTIB and NCI Frederick Genomic Core Facility (Storage at CSP)
RNA expression level of 770 genes				LTIB and NCI Frederick Genomic Core Facility
Soluble Factors (to include sCD27 and sCD40 ligand) by ELISA	8 mL blood for serum	SST		LTIB (Storage at CSP)
M7824 Pharmacokinetics	4 mL blood for serum	SST		EMD Serono (Storage at BPC)
ADA by ELISA	4 mL blood for serum	SST		EMD Serono (Storage at BPC)
AVA by ELISA	1 mL blood for serum	SST		Precigen (Storage at BPC)
Immune Markers by IHC	Tumor samples	N/A		GMB TIME LAB (Storage at LP, CSP)
Single-cell Proteomic analysis	Tumor samples	N/A		Precigen (Storage at LP, CSP)

Abbreviated Title: Combo Immunotx in HPV OPSCC

Version Date: 09.20.2023

Test/assay	Volume (approx.) per Timepoint	Type of tube ^a	Collection point	Location of specimen analysis
Immune transcriptomic analysis	Tumor samples	N/A		Precigen (Storage at LP, CSP)
RNA expression level of 770 genes	Tumor samples	N/A		LTIB and NCI Frederick Genomic Core Facility (Storage at LP, CSP)
HPV status by PCR of DNA	Tumor samples	N/A		[name] (Storage at LP, CSP)
Circulating free tumor DNA (cfDNA) by PCR system	Plasma	EDTA (lavender top)		LTIB and NCI Frederick Genomic Core Facility (Storage at CSP)
T cell clonality by immunoseq platform	Tumor samples	N/A		LTIB and NCI Frederick Genomic Core Facility (Storage at LP, CSP)
Salivary HPV DNA	15-20 mL 0.9% NaCl rinse	50 mL conical tube		LTIB and NCI Frederick Genomic Core Facility (Storage at CSP)

^a Please note that tubes and media may be substituted based on availability with the permission of the PI or laboratory investigator.

Research blood samples will be sent either to the Clinical Services Program – Leidos Biomedical Research, Inc. (CSP) (Section 5.2.1) or the Blood Processing Core (BPC) (Section 5.2.2) for barcoding, initial processing and storage. Tissue will be sent to the Laboratory of Pathology as described in Section 5.2.3. Additional tissue for research may also be stored in CSP (Section 5.2.1). From these facilities, coded, linked samples will be sent to the designated labs for analysis upon request.

